A more relevant drug to the question of chronic pain after surgery is gabapentin, and some clinical trials have suggested that perioperative treatment of this drug can reduce the incidence of this problem (Schmidt, 2013). In the NIH application we propose to test gabapentin rather than modafinil because our previous work with direct measures in rats and cerebrospinal fluid norepinephrine sampling in humans is consistent with gabapentin activating LC in both species (Hayashida, 2007). The pupil measurements in this feasibility study will more directly assess whether gabapentin does indeed increase LC activity in humans. Should it fail to demonstrate a reasonable effect size to dilate the pupil, we will revise the NIH application to study modafinil rather than gabapentin. As such, these preliminary data are very important to the design of the final study.

Study Design.

Hypotheses: (1) Gabapentin and modafinil will increase resting pupil diameter with a moderate effect size in patients with osteoarthritis; (2) Expectations will modify pain experience with a moderate effect size in these patients

Study design: Single-center, randomized, controlled study of gabapentin, modafinil, and placebo in 30 subjects (10 per group) with moderate osteoarthritis pain of the hip or knee or healthy individuals without pain

Primary outcome measures: (1) Resting pupil diameter and response to noxious stimuli after study drug; (2) Interaction between resting pupil diameter and correlation of cognitive-affective state to pain reporting.

Inclusion criteria: Adult, nonpregnant adults scheduled with moderate pain (verbal score of $\geq 4 \leq 7$ on 0-10 scale for average pain intensity with normal activity) from osteoarthritis of the knee or hip, or healthy individuals without pain, American Society of Anesthesiologists physical status 1-3, able and willing to perform the study procedures, including sitting in a chair for 45 min. Individuals must be able to read.

Exclusion criteria. (1) Inability to complete questionnaires; (2) Pregnancy; (3) Currently taking gabapentin or > 50 mg morphine equivalents/day; (4) advanced or unstable cardiac, pulmonary, renal or hepatic dysfunction; (5) history of previous eye surgery; (6) psychotic disorder or a recent psychiatric hospitalization.

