Data analysis. Pupil diameter data will be conditioned to remove blink and saccade artifacts and smoothed using an autoregressive filter. The local resting diameter will be determined representing the average smoothed value for the 500 msec preceding the stimulus onset. The pupil response to each stimulus is calculated as the mean pupil diameter during the 5 sec stimulus after accounting for lag time from onset of stimulus to onset of pupil response and is expressed as a % change from the local resting diameter (see our preliminary data for examples). Multidimensional Scaling (MDS) will be used to create a single dimensional scale from the catastrophizing and optimism scores (i.e., responses from these two questionnaires will be weighted and scaled to create a single-dimensional construct)

To determine the interaction among the factors of interest, and to accommodate the many repeated measures within each participant, we will utilize Generalized Estimating Equations. In our experience, the pupil response to painful stimuli is well modeled by a normal distribution with an identity link and an AR1 repeated measures covariance structure. To examine our hypotheses, we will model percent pupil change (the DV) using fixed effects for stimulus temperature, catastrophizing-optimism score (i.e., cognitive-affective state), and pre-stimulus baseline pupil diameter (i.e., LC activity). The association between cognitive-affective state and pain reporting will first be examined, and in a later block the moderating effect of baseline pupil size will be entered.

The goal of this feasibility study is to estimate the effect size of drugs on pupil diameter and the strength of interaction between pupil diameter and the relationship between cognitive-affective state.

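### The evoked pupil response is a percentage of the resting diameter and is then modelled on that same diameter, so its baseline coefficient and any unadjusted drug contrast depend on an unstated scaling assumption

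*Protocol*

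**What the plan says.** All of the relevant definitions are in the Protocol.

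- **Resting diameter (Data analysis).** The local resting diameter is "the average smoothed value for the 500 msec preceding the stimulus onset".
- **Response (Data analysis).** It is the lag-adjusted mean diameter over the 5 s stimulus, and it "is expressed as a % change from the local resting diameter".
- **Model (Data analysis).** "we will model percent pupil change (the DV) using fixed effects for stimulus temperature, catastrophizing-optimism score (i.e., cognitive-affective state), and pre-stimulus baseline pupil diameter". That last predictor is glossed as LC activity. The response is said to be "well modeled by a normal distribution with an identity link and an AR1 repeated measures covariance structure", fitted by GEE. No drug term is listed.
- **Outcome (Study Design, Primary outcome measures).** Primary outcome 1 is "Resting pupil diameter and response to noxious stimuli after study drug".
- **Expected drug effect (Study Design, Hypotheses).** "Gabapentin and modafinil will increase resting pupil diameter with a moderate effect size". Expected results repeats the direction.

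The SAP specifies two mixed models: tonic diameter on drug, time and their interaction, and VAS pain on cognitive style, tonic diameter and their interaction. It neither redefines nor analyses the evoked response, so the Protocol's percentage measure is the only definition of that part of primary outcome 1.

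**The concern.** One short measurement does three jobs: it is subtracted from the stimulus-period diameter, it divides the difference, and it is the predictor given a mechanistic reading. A negative coefficient for that predictor could then come from the construction of the variable and still be read as biology, with high tonic LC activity going with a weak phasic response.

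The same denominator is what the study drugs are expected to raise. If someone compares percentage responses between arms without adjusting for baseline, part of the difference can be the change in denominator. The study exists to supply effect sizes and variability for a later trial, so bias in an estimate matters here even where no test would detect it.

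**Working it through.** The documents give no SD, no dilation in mm and no power calculation, so there is no stated figure to reproduce. Figures 2 and 3 were not available for this check. All mm values and CVs below are assumptions.

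**1. Algebra.** Let B be the resting diameter and D the dilation in mm, so the response is 100·D/B. Suppose D = c + kB.

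- Response = 100c/B + 100k, with slope on B of −100c/B².
- Exactly proportional dilation (c = 0): slope 0.
- D independent of B, at B = 5 mm and D = 0.4 mm (c = 0.4): −100 × 0.4/25 = −1.6 percentage points per mm.
- Half-proportional dilation (c = 0.2): −100 × 0.2/25 = −0.8 points per mm.

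**2. Correlation when mm response is independent of baseline.** One million draws of B ~ N(1, CV_B) and independent response ~ N(1, CV_D). As CV_B goes from 10% to 20%, the correlation of the ratio with B goes from −0.20 to −0.39 at CV_D = 50%, and from −0.32 to −0.57 at CV_D = 30%.

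**3. Denominator shift between arms, equal mm dilation, unadjusted.** Relative fall = 1 − 1/(1 + d × CV_B), where d is the drug effect on resting diameter in SDs.

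- d = 0.5: 1 − 1/1.05 = 4.8% (CV 10%); 1 − 1/1.10 = 9.1% (CV 20%).
- d = 0.8: 1 − 1/1.08 = 7.4%; 1 − 1/1.16 = 13.8%.

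**4. Simulated baseline slope.** 30 subjects with 20 stimuli each (the analysed pre-drug count: four sequences of five), 400 runs per setting. Assumed: resting mean 5 mm, between-subject SD 0.8, within-subject SD 0.3; dilation 0.25 mm at 47 °C and 0.5 mm at 50 °C, with between-subject log-SD 0.3 and trial noise 0.15 mm. The fit was GEE with robust SE and an independence working correlation, not the planned AR1. In brackets is the share of runs with p < 0.05.

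| True mm dilation | Baseline error SD | Slope of % response (points per mm) | Between-subject r of % response | Slope of mm change (mm per mm) |
|---|---|---|---|---|
| Independent of B | 0 | −1.71 (87%) | −0.45 | 0.00 (11%) |
| Independent of B | 0.2 mm | −3.01 (100%) | −0.48 | −0.06 (57%) |
| Proportional to B | 0 | −0.04 (10%) | −0.01 | +0.08 (87%) |
| Proportional to B | 0.2 mm | −1.29 (65%) | −0.02 | +0.02 (13%) |

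Rates of 10% to 11% where the slope is essentially zero reflect the robust SE with only 30 clusters. Two things follow. Under proportional dilation, baseline error alone still gives a negative percentage slope, but it acts within subjects and leaves the between-subject correlation near zero. And changing to mm does not by itself remove the shared error.

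**5. Simulated drug contrast.** Two arms of 10, 4,000 runs, resting shift 0.4 mm (0.4/0.8 = 0.5 SD), dilation 0.4 mm, no baseline error.

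- Equal mm dilation, % response: −0.67 points unadjusted (sampling SD 1.32, so 0.67/1.32 = 0.51 SD); 0.00 with baseline as covariate.
- Equal mm dilation, mm response: 0.00 either way.
- Proportional dilation: % response −0.02 unadjusted; mm response +0.03 mm unadjusted and 0.00 adjusted.

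**The case against.** The strongest case on the other side has four parts.

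- **The artefact is conditional.** A reader might infer that a person or arm with a larger resting pupil must show a smaller percentage response by arithmetic alone. The documents do not support that. It requires mm dilation that grows less than in proportion to resting size, and no mm data are given. This stands. What remains is that exact proportionality is the one neutral case, and the plan neither claims nor tests it.
- **No specified analysis contains the drug artefact.** A reader might infer that an effective drug will appear to blunt the response. The Protocol's percentage model has no drug term, and if drug were added, the baseline covariate already there would bring the contrast to about zero under equal mm dilation. This stands too. The residual risk is that nothing prespecifies how the post-drug response will be compared, adjusted or not.
- **Reach is narrow.** A reader might infer that the main conclusions are compromised. Neither SAP model uses the percentage response, and the Protocol ties the choice between gabapentin and modafinil to dilation of the pupil, not to the evoked response. This stands in full.
- **Moving to mm is no cure.** Under proportional dilation the mm scale creates the opposite slope, and mm change regressed on the same baseline keeps the shared error. This stands and shapes the fix.

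**Conclusion.** The point holds in conditional form and is worth a cheap correction. The percentage response shares a term with its predictor, the scale is not justified, and the baseline coefficient cannot be read as LC biology.

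- **Baseline coefficient.** If mm dilation is independent of resting size, the false slope is about −1.7 points per mm under the assumed values, and about −3.0 with a baseline error SD of 0.2 mm. If dilation is proportional, only the error component remains, mainly trial by trial.
- **Drug contrast.** The relative fall of 4.8% to 9.1% applies only to an unadjusted percentage comparison, with equal mm dilation, d = 0.5 and an assumed baseline CV of 10% to 20%. In the simulated case it is about half a sampling SD at 10 per arm: a modest bias in an effect-size estimate, not a likely false-positive test.
- **Scope.** It is confined to the evoked-response half of primary outcome 1, for which the SAP has no analysis.

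**What to change.** Add an analysis of the evoked response to the SAP:

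1. **Model.** Outcome: lag-adjusted stimulus-period mean diameter in mm. Covariate: pre-stimulus resting diameter. Fixed effects: stimulus temperature, drug, time and drug × time. Keep a repeated-measures structure within subject.
2. **LC marker.** Where resting diameter is interpreted as LC activity or as a moderator, take it from a separate resting window, for example the subject- or sequence-level tonic diameter, and not from the same 500 ms. State the window; the SAP uses tonic diameter without defining one.
3. **Reporting.** Give percentage change alongside as a secondary, scale-sensitivity result, and do not interpret the baseline coefficient of the percentage model.
4. **Unadjusted contrast.** Also give the drug contrast in mm without the baseline covariate.

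Step 1 gives the same drug, time and temperature coefficients as mm change with baseline as covariate in a linear model. Only the baseline slope differs, by exactly 1 (for example 1 − 0.06 = 0.94), so shared error still distorts that slope. This is why step 2 is needed.

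The cost is a short SAP paragraph and one extra derived variable, with no new measurements. Results compare less directly with preliminary percentage figures, which step 3 mitigates. The adjusted drug contrast conditions on a baseline that the drug may itself change, which is the reason for step 4.

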A Feasibility Study: Understanding and Altering Pain Expectations in Subjects With  
Osteoarthritis of the Knee or Hip  
Statistical Analyses Plan

NCT02155257

11/02/2018

To address the two primary hypotheses, linear mixed effects models will be employed. For each model, subject will be specified as a random effect to account for the repeated measures within individuals. To examine the impact of drug (i.e., placebo, gabapentin, modafanil) on tonic pupil diameter, pupil diameter will be regressed on fixed effects for drug, time (i.e., pre-drug vs post-drug), and a drug x time interaction. A group x time integration would be interpreted as evidence supporting the hypothesis that drug differentially impacted baseline pupil over time.

To examine the impact of tonic pupil diameter on the relationship between cognitive style (i.e., catastrophizing-optimism dimension) and pain reporting, VAS scores will be regressed on fixed effects for catastrophizing-optimism, tonic pupil diameter, and the interaction between catastrophizing-optimism x pupil diameter. A statistically significant interaction would be interpreted as evidence that tonic pupil diameter moderated the relationship between cognitive style and pain reporting. Where appropriate, all analyses are two-tailed with statistical significance interpreted at  $p < 0.05$ . The analyses will be conducted using R 3.4 and R Studio.

The sample size was based on estimating the feasibility of the protocol and on establishing effect size estimates. No formal statistical power calculations were conducted.

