In this ongoing study we have examined pupil responses to phasic noxious heat stimuli to date in 19 normal volunteers and 4 subjects with migraine (but not in the presence of a headache). Studies were performed in a room with constant, low ambient light so that both constriction and dilation of the pupil could be observed. Pupil diameter was continuously monitored by an infrared camera (Eye-Trac™ system; Applied Science Laboratories) with the subject's chin resting on a chin rest and gaze on a fixed object presented on a monitor. A 4 cm² Peltier-controlled thermode was placed on the calf, with temperature maintained at 35°C and 5 sec stimuli at various temperatures applied every 30 sec. Subjects reported pain intensity with a visual analog scale (VAS) from 0 (no pain) to 100 (worst pain imaginable). Increasing probe temperature to 50°C resulted in pain report and pupil dilation, the former with a longer lag (Figure 2, typical response). As previously described with other stimuli (Chapman, 1999; Oka, 2007), there was a direct relationship between pupil dilation and noxious heat temperature as well as VAS pain intensity and unpleasantness.

We next examined the relationship between pupil response and pain report as a function of affective distress. We estimated affective distress as the sum of scores to the pain catastrophizing scale, the CSED depression scale, the state trait anxiety inventory, and the pain anxiety symptom scale and linearly regressed this on pain report. The residual from the regression line for each individual was related to baseline pupil diameter as a measure of tonic LC activity. Despite there being a very small range of affective distress in this largely normal population, the residual (tendency to adhere to cognitive-affective state in pain reporting) was significantly related to baseline pupil diameter (Figure 3).

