Five sequences of test stimuli will be presented, with a brief break in between each sequence (Figure 5A). The first sequence will consist of 7 stimuli, from 39° to 51° C in 2° C increments, in ascending order. Data from this training sequence will not be used for analysis. Sequences 2 and 3 will consist of 5, 5-sec stimuli, presented in random order, to generate moderate (50° C) and mild (47° C) pain (random condition). Sequences 4 and 5 will also consist of random presentation of 5 stimuli at these temperatures, but with different auditory tones 6 s prior to stimulus onset to correctly cue the stimulus temperature (cued condition).

Subjects will then be randomized to receive oral gabapentin, 900 mg, modafinil, 200 mg, or placebo, followed 2 hr later by pain testing with pupillometry, consisting of different sequences (Figure 5B). The random and cued paradigms will be presented twice each (only 1 representative shown in Figure 5B), followed by a sequence with one miscue in the positive expectation for pain direction (signal for 50° C but deliver 47° C) and one in the negative

Table 1. Questionnaires

Stanford Expectations of Therapy Scale
WOMAC- Osteoarthritis Index
Life Orientation Test-Revised (LOT-R)
PROMIS- Depression
PROMIS- Anxiety
Pain Medication Attitudes Questionnaire (PMAQ)
Pain Locus of Control Scale (PLOC)
Pain Self-Efficacy Scale (PSE)
Barratt Impulsivity Test
Fear of Pain Questionnaire
Pain Catastrophizing Scale (PCS)
Tampa Scale of Kinesiophobia (TSK)

[figure not shown]

Figure 4: The dimensional structure of the continuum of cognitive style to be used, including psychosocial constructs associated with each end.

expectation for pain direction (mistrust condition, yellow bars in Figure 5B). Subjects will provide verbal pain intensity scores after each stimulus.

The pre-drug and post-drug set of sequences will take approximately 30-40 min including breaks between sequences of stimuli. Following this subjects will be discharged from the clinical research unit accompanied by a responsible adult.

[figure not shown]

Figure 5: Heat stimuli give before (A) or after (B) study drug

Subject payment. Subjects will be paid \$250 for participation in the study.

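### The SAP does not fix the data row for its drug-by-time model; on per-stimulus rows with only a random subject intercept, drift or positive serial correlation makes the drug effect's standard error too small

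*SAP*

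**What the plan says.** **SAP, first primary analysis.** The model terms are: "pupil diameter will be regressed on fixed effects for drug, time (i.e., pre-drug vs post-drug), and a drug x time interaction". The random part is: "For each model, subject will be specified as a random effect to account for the repeated measures within individuals". The SAP does not define the row of the data set, an averaging step, a subject-by-time random effect or a residual correlation structure.

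**Protocol, Data analysis.** Resting diameter is defined stimulus by stimulus: "The local resting diameter will be determined representing the average smoothed value for the 500 msec preceding the stimulus onset". The same section uses this pre-stimulus value as its measure of LC activity.

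**Protocol, Study procedures.** Before drug: "Five sequences of test stimuli will be presented, with a brief break in between each sequence". The first sequence is training and is not analysed. For the next two: "Sequences 2 and 3 will consist of 5, 5-sec stimuli, presented in random order". Sequences 4 and 5 also have 5 stimuli each. Stimuli are 30 sec apart. Study drug is given once, "followed 2 hr later by pain testing with pupillometry". After drug, the random and cued paradigms are each run twice and one miscued sequence follows; the lengths of these sequences are not given.

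**Protocol, Background.** The preliminary work uses the pupil at subject level: "The residual from the regression line for each individual was related to baseline pupil diameter as a measure of tonic LC activity".

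**The concern.** Each subject is randomised to one drug and dosed once. The drug-by-time effect is therefore a comparison between arms of subjects' pre-post changes, and its error term should be the variation of that change between subjects: 27 df with 10 per arm. Repeated readings within a session sharpen each subject's mean but add no subjects.

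If the rows are stimuli and the only random term is a subject intercept, the interaction is instead tested against trial-to-trial scatter. That is right only if every subject's true change within an arm is the same and readings within a session are independent given the subject. Sessions some two hours apart and readings 30 sec apart make departures from both plausible, although the documents give no data on either.

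The Protocol says the study is to estimate the size of the drug effects on the pupil and to supply variability figures for powering a later trial. The SAP also reads the interaction as evidence for the drug hypothesis, with significance at p < 0.05. An understated SE would affect that test and the interval around each effect size. The fit on stimulus rows would also not estimate the between-subject SD of change, which the later power analysis needs.

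**Working it through.** The plan has no figure of its own to reproduce: the SAP states that no power calculation was made.

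**Inputs from the documents.** 3 arms × 10 = 30 subjects; two-sided 5%; 4 sequences × 5 = 20 analysed readings before drug.

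**Assumptions.** 20 readings after drug (25 if the miscued sequence also has 5 and is included); per-stimulus rows; random subject intercept only; no true drug effect; trial-to-trial SD = 1. Drift SD τ, the between-subject SD of true pre-post change, is varied because the documents give no pupil variance components.

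**Degrees of freedom.** 30 × 40 = 1,200 rows. The random-intercept model tests the interaction on 1,200 − 30 − 3 = 1,167 df, against 30 − 3 = 27 for subject-level changes.

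**Closed form, no serial correlation.**
- True variance of a subject's mean change: τ² + 2/20 = τ² + 0.1.
- Variance the model implies: 0.1 × s², where s² = [30 × 38 + 27(1 + 10τ²)]/1,167.
- Understatement factor: R = (τ² + 0.1)/(0.1 s²).
- The test has 2 numerator df and a critical F of about 3.00, so null rejection is roughly exp(−3.00/R).

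The last two columns come from 20,000 simulated null trials per row.

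| τ | s² | R | SD of change: true / implied | exp(−3.00/R) | Simulated rejection | 95% CI coverage, one contrast |
|---|---|---|---|---|---|---|
| 0 | 1.00 | 1.00 | 0.32 / 0.32 | 5.0% | 5.1% | 94.9% |
| 0.1 | 1.00 | 1.10 | 0.33 / 0.32 | 6.5% | 6.4% | 94.1% |
| 0.25 | 1.01 | 1.60 | 0.40 / 0.32 | 15.3% | 15.2% | 87.9% |
| 0.5 | 1.06 | 3.31 | 0.59 / 0.33 | 40.4% | 40.7% | 71.8% |
| 1.0 | 1.23 | 8.93 | 1.05 / 0.35 | 71.5% | 72.0% | 48.8% |

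The residual variance s² stays at 1.00 to 1.23 against a true 1, so the fault lies in the SE of the contrast. With 25 post-drug readings, rejection at τ = 0.25, 0.5 and 1.0 is 16.5%, 43.5% and 73.7%.

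**Serial correlation, no drift.** With AR1 of 0.3, 0.5 and 0.7 running through each session, rejection is 19.2%, 36.3% and 58.1%. If the correlation restarts after each break between sequences, it is 15.6%, 27.2% and 40.3%. With AR1 of −0.3 it is 0.4%, so the test is then conservative.

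**Condition effects.** A shift common to all subjects, between random and cued sequences, cancels from the contrast in a balanced layout but inflates s² if it is not modelled. An assumed 1-SD shift adds 0.25 × 1,200/1,167 = 0.26. At τ = 0.5, R becomes 0.35/(0.1 × 1.315) = 2.66 and exp(−3.00/2.66) = 32%. Simulation gives 32.5%, instead of 40.1% without the shift.

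**Subject-period means.** With one mean per subject per period, rejection is 4.8-5.5% in all these drift and AR1 settings.

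**Fitted mixed models (400 simulated trials, τ = 0.5).** Both layouts return the same contrast estimate. The mean reported SE is 0.145 on stimulus rows and 0.261 on subject-period means; the actual SD of the estimate is 0.260.

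**The case against.** The strongest reply is that this is an unstated detail and not a demonstrated error. The SAP calls its outcome tonic or baseline pupil and gives time two levels. The Protocol's Background relates baseline pupil to one residual per individual. The per-stimulus quantity has a different name and also serves as the reference for each stimulus's percentage change. In cued sequences the tone sounds 6 s before the stimulus, so the 500 msec window follows a cue and is a doubtful measure of tonic diameter. On the subject-mean reading the SAP model is valid. The SAP also does not say that the subject effect is an intercept only.

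This stands as far as it goes: a reader might infer that the planned analysis is invalid, and the documents do not support that. But the per-stimulus definition is the only operational one, no averaging step is given and no subject-by-time term is stated. An analyst could follow the plan to the letter and obtain the understated SE.

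Three further inferences should be resisted:
- **That any serial correlation shrinks the SE.** Only positive correlation does.
- **That the simulated rates describe this trial.** They rest on assumed values. The Protocol's AR1 remark concerns percentage pupil response under GEE, not resting diameter.
- **That the drug choice or the next trial's sample size must be wrong.** The point estimate is unaffected in balanced data, and the Protocol says the study is not powered for definitive drug effects. A later sample size suffers only if its planner takes this model's SE at face value.

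**Conclusion.** The concern holds conditionally and should be fixed. The harm needs three things together: per-stimulus rows, no subject-by-time term or equivalent, and subject-specific drift or positive serial correlation. The plan permits the first two and rules out none of them. Under those conditions the drug effect's SE is too small, its 95% CI too narrow and its p-value too small.

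The size here is unknown. For drift SDs of 0.25, 0.5 and 1.0 times the trial-to-trial SD, the contrast variance is understated 1.6, 3.3 and 8.9 times. At zero drift and no serial correlation there is no material error. These figures assume 20 readings per period and no condition effects in the residual; such effects would reduce them. Confidence is medium, because the text leaves the row open.

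**What to change.** Add to the SAP that the outcome is one mean resting diameter per subject per period, entered in the existing drug-by-time model. This needs no assumption about drift or serial correlation.

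If stimulus rows are kept, add a by-subject random slope for time, allow for serial correlation within session, and use subject-level denominator df.

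Under either option, report the gabapentin-placebo and modafinil-placebo differences in change with 95% CIs, and the between-subject SD of pre-post change for the later power analysis.

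The cost is SAP wording only, with no new data. With no drift or serial correlation, intervals widen by about 4-5% (t quantile 2.05 on 27 df against 1.96 on 1,167 df; 2.05/1.96 = 1.05). At drift 0.25, 0.5 and 1.0 they are about 1.3, 1.9 and 3.1 times as wide (√R × 1.05), which is the uncertainty that 10 subjects per arm carry under those assumptions.

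### The drug-by-time model is a change-score comparison; adjusting for pre-drug pupil diameter would usually give a more precise drug effect at almost no cost

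*SAP*

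**What the plan says.** The SAP (unnumbered, first paragraph) states that "pupil diameter will be regressed on fixed effects for drug, time (i.e., pre-drug vs post-drug), and a drug x time interaction", and that "subject will be specified as a random effect to account for the repeated measures within individuals". A drug-by-time interaction "would be interpreted as evidence supporting the hypothesis that drug differentially impacted baseline pupil over time". Pre-drug diameter is therefore one level of the outcome. The SAP names no baseline covariate and does not constrain the arms to a common pre-drug mean. It does not say whether the model is fitted to single readings or to subject means.

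The protocol (Study procedures) runs the pre-drug stimulus sequences first and then says "Subjects will then be randomized to receive oral gabapentin", modafinil or placebo. The Study design section plans 30 subjects, 10 per arm.

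No other section supplies a baseline-adjusted drug effect. The GEE under Data analysis in the protocol models percent pupil change and lists no drug term. Its baseline diameter is the reading just before each stimulus, not the pre-drug value.

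The protocol hypothesises that "Gabapentin and modafinil will increase resting pupil diameter with a moderate effect size" but gives no number for it. Neither document gives an SD or a pre-post correlation for pupil diameter, and the SAP says that no power calculation was done.

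**The concern.** Randomisation follows pre-drug testing, so any pre-drug difference between arms is chance. The planned model still estimates a separate pre-drug mean for each arm and subtracts it in full. Unless the regression of post-drug on pre-drug diameter has a slope of 1, full subtraction removes too much. An arm that happens to start with larger pupils will tend to show too small a drug effect, and an arm that starts smaller will tend to show too large a one.

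Precision matters here because the drug effect size is the trial's main product. The protocol's Data analysis section gives its estimation as the goal. The Background makes the choice between gabapentin and modafinil for the grant application depend on it. The Expected results section says the data will feed the power analysis of the later study.

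**Working it through.** **Inputs.** From the documents: 10 subjects per arm, three arms, one pre-drug and one post-drug period. Assumed, because the documents give no values: equal SDs before and after drug (set to 1), and a correlation r between subject-mean pre- and post-drug diameters of 0.5, 0.7, 0.9 or 0.95. The plan has no power figure to reproduce.

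**Step 1: what the interaction estimates.** The planned model was fitted to simulated data with one value per subject per period. The two interaction coefficients (0.0177 and 0.5900) equalled the differences in mean change from placebo. With 20 readings per period the coefficient checked (−0.7806) again equalled the difference in mean change. The interaction is a change-score contrast.

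**Step 2: variance per subject.**
- Change score: 2(1 − r).
- Adjusted for the pre-drug value (ANCOVA): 1 − r².
- Ratio, adjusted to change: (1 + r)/2, so the large-sample saving is (1 − r)/2.

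**Step 3: cost of estimating the slope.** With 30 subjects in 3 arms, the adjusted variance rises by the factor 1 + 1/(30 − 3 − 2) = 1.04. The net saving is 1 − 1.04(1 + r)/2. It reaches zero at r = 2/1.04 − 1 = 0.92.

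**Step 4: results.** The standard error of a drug-placebo contrast, in SD units, is √(2/10 × variance), with the 1.04 factor included for the adjusted analysis.

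| r | Change | Adjusted | Large-sample saving | Net saving, 10 per arm | SE, change → adjusted |
|---|---|---|---|---|---|
| 0.5 | 1.00 | 0.75 | 25% | 22.0% | 0.447 → 0.395 |
| 0.7 | 0.60 | 0.51 | 15% | 11.6% | 0.346 → 0.326 |
| 0.9 | 0.20 | 0.19 | 5% | 1.2% | 0.200 → 0.199 |
| 0.95 | 0.10 | 0.0975 | 2.5% | −1.4% | 0.141 → 0.142 |

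A simulation of 20,000 trials at each of r = 0.5, 0.7 and 0.9, with 10 per arm, gave net savings of 21.3%, 11.1% and 1.3%.

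**Step 5: chance imbalance.** Given a pre-drug difference d between two arms, the change-score estimate shifts by −(1 − r)d. The simulated slopes on d were −0.49, −0.30 and −0.10 at r = 0.5, 0.7 and 0.9, against about 0 for the adjusted estimate. One standard error of d is √(2/10) = 0.45 SD, so the typical shift is (1 − r) × 0.447 = 0.22, 0.13 or 0.04 SD. This is not a second harm: 2(1 − r) − (1 − r²) = (1 − r)², so the excess variance in Step 2 is exactly the variance of this shift.

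**Step 6: the common-pre-drug-mean alternative.** One could keep the longitudinal model and drop the drug main effect. With only a subject random intercept (variance τ²), residual variance σ² and m pre-drug readings, that model puts weight w = mτ²/(mτ² + σ²) on the pre-drug mean. Sequences 2–5 of 5 stimuli each give m = 20. Under assumed levels of reading noise, w then came out at about 0.92–0.98, close to the change score's weight of 1. The variance is 1 + w² − 2wr:
- r = 0.5: 0.980 (w = 0.98) or 0.926 (w = 0.92) against 1.00, a saving of 2–7%.
- r = 0.7: 0.588 or 0.558 against 0.60, again 2–7%.

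Most of the gain is lost if that model is fitted to single readings without a further random effect.

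**The case against.** The strongest defence is that nothing here is invalid. The interaction contrast is unbiased over randomisation. The protocol's Expected results section says that the study is not powered to settle the drug effects, and the model still yields changes by arm. Both periods fall in one visit, about two hours apart, with the same lighting and head position. Averaging about 20 readings per period also removes reading noise. All of this could push r towards the end where adjustment gains little. For an assumed effect of 0.5 SD, normal-approximation power moves only from 20% to 24% (r = 0.5), from 30% to 34% (r = 0.7), or not at all from 71% (r = 0.9).

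That stands as an argument about importance. It does not favour the change score, because r is unknown and the loss from adjusting at high r is about 1%, against a gain of about a fifth of the variance at r = 0.5.

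A reader might infer four stronger claims, none of which holds:
- **That the plan is known to waste 5–25% of the variance.** Those are large-sample figures for an assumed r of 0.9 to 0.5. With 30 subjects the range is about 1–22%, and no value of r is in the documents.
- **That chance imbalance is left in the estimate and biases it.** The model over-corrects for imbalance, and the errors average out over randomisation.
- **That imbalance is a further cost on top of lost precision.** Step 5 shows that they are the same quantity.
- **That dropping the drug main effect is automatically equivalent to ANCOVA.** Step 6 shows that it depends on the random-effects structure.

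**Conclusion.** The point holds as a cheap improvement. The SAP's drug effect is a change-score contrast, valid as an estimate but usually less precise than one conditioned on a pre-drug value that is already collected before randomisation. With 10 per arm and equal SDs, adjustment saves about 21–22%, 11–12% or 1% of the variance at r = 0.5, 0.7 or 0.9, and loses about 1% at r = 0.95. The size rests entirely on r and on the equal-SD assumption, neither of which the documents settle. In large samples the direction does not depend on equal SDs: with SDs s₀ before and s₁ after drug, the excess variance of the change score is (s₀ − r·s₁)², which is never negative.

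**What to change.** Replace the primary drug analysis in the SAP's first paragraph with wording such as: *The drug effect on tonic pupil diameter will be estimated by regressing each subject's mean post-drug diameter on drug and mean pre-drug diameter, with 95% confidence intervals for each drug versus placebo.* Keep the drug-by-time model as a sensitivity analysis.

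If a longitudinal model with a common pre-drug mean is preferred, fit it to one mean per subject per period, or add a subject-by-time random effect when single readings are modelled. Stating the unit of analysis also helps with a separate issue: with single readings, a random intercept alone may understate the interaction's standard error (0.085 against 0.318 from subject means in one simulated data set).

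The cost is a change of wording and one error degree of freedom. No new data are needed, and the precision loss is negligible if r turns out to exceed about 0.92. Reporting the observed r and SDs would also serve the planning of the later study.
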